#### **Primary Analysis**

The objectives of the primary analysis are to determine the MTD for each formulation of oprozomib in combination with pomalidomide and dexamethasone and further evaluate the safety and tolerability of the OPomd combination in subjects with relapsed or refractory multiple myeloma. In addition, this analysis will be used, as possible, to recommend the most appropriate oprozomib dose and formulation to be tested in future clinical trials in an OPomd combination, based on safety, tolerability, efficacy, PK and other available data from all the escalation cohorts.

The primary analysis will be based on subject data collected up to two months from the date of last subject enrollment. A Bayesian 2-parameter logistic regression model, the NCRM will be applied to observed DLTs to find MTDs for the oprozomib formulations (Neuenschwander, 2008). The prior distribution and the data available after each dose cohort are applied to the algorithm that computes the posterior distribution of the DLT rate at each dose level. The posterior probabilities of the estimated DLT rate at each dose to fall into target toxicity interval (15% to 25%) or excessive/unacceptable toxicity interval (> 25% to 100%) will be used in the dose escalation decision and the final determination of the MTD. Refer to study design section for a detailed description of the dose escalation method. The safety analyses will be based on the safety evaluable population, which is defined as all subjects who received any amount of the study treatment regimen oprozomib, dexamethasone and pomalidomide. Safety and tolerability will be assessed through summaries of study drug administration, DLTs, adverse events, changes in selected laboratory analytes, and vital signs by dose level.

The primary efficacy analysis will be performed in all subjects that received at least one cycle of OPomd and have baseline disease assessment and at least one post-baseline disease assessment. Both overall response rate and the best overall response will be summarized.

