##### **13.1.2 Analysis Sets**

The safety population is defined as all subjects who receive any amount of oprozomib, pomalidomide and/or dexamethasone.

The efficacy population is defined as subjects who are included in the safety evaluable population, and have a baseline disease assessment and at least 1 post-baseline disease assessment.

PK population is defined as subjects for whom at least 1 PK parameter can be adequately estimated.

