### 13.3.2 Primary Analysis

The main objectives of the primary analysis are to determine the MTD for each formulation of oprozomib in combination with pomalidomide and dexamethasone and further evaluate the safety, tolerability and efficacy of the OPomd combination in subjects with relapsed or refractory multiple myeloma. The primary analysis will be based on subject data collected up to two months from the date of last subject enrollment. In addition, this analysis will be used to possibly recommend the most appropriate oprozomib dose and formulation to be tested in future clinical trials in an OPomd combination. The selection of the oprozomib recommended dose and formulation will be based on all data from the escalation cohorts.

Safety and tolerability will be assessed through summaries of study drug administration, DLTs, adverse events, changes in selected laboratory analytes, vital signs, and physical findings by dose level. Means and standard deviations will be used to summarize the total dose for each component of study drug received. All summaries will be presented by the assigned dose level and for all subjects.

All adverse event data will be listed by study site, dose level, subject identification number, and study day. All adverse events will be summarized by preferred term, appropriate thesaurus levels, and CTCAE (Version 4.03) toxicity grade. In addition, all serious adverse events, including deaths, will be listed separately and summarized.

Efficacy analyses of ORR and BOR will be performed using both the efficacy and safety population as defined previously.

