#### 13.4.3.2 Efficacy Endpoints

All efficacy assessments will follow IMWG uniform response criteria and be performed every 4 weeks ( $\pm$  1 week).

Overall response rate (defined as the proportion of best overall response of stringent complete response [sCR], complete response [CR], very good partial response [VGPR], and partial response [PR]), best overall response, PFS (defined as the number of months from subject's first study dose date to the earlier of disease progression or death due to any cause), and DOR will be summarized for all subjects overall, by formulation, by dose cohort level, and by formulation and dose cohort level along with 95% confidence intervals when applicable.

All subjects who receive treatment with any amount of the OPomd and have a baseline disease assessment and at least 1 post-baseline disease assessment will be included in the efficacy analyses. Additional efficacy analyses will be performed based on subjects who receive treatment with any amount of OPomd.

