6.2 Efficacy Analysis Set

The efficacy population is defined as subjects, **excluding roll-over subjects**, who are included in the safety evaluable population, and have a baseline disease assessment and at least 1 post-baseline disease assessment.

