9.5.2 Analyses of Secondary Efficacy Endpoint(s)

Overall response rate (defined as the proportion of best overall response of stringent complete response [sCR], complete response [CR], very good partial response [VGPR], and partial response [PR]), best overall response, PFS (defined as the number of months from subject's first study dose date to the earlier of disease progression or death due to any cause), and DOR will be summarized for all subjects overall, by formulation, by dose cohort level, and by formulation and dose cohort level along with 95% confidence intervals when applicable.

All subjects who receive treatment with any amount of the OPomd and have a baseline disease assessment and at least 1 post-baseline disease assessment will be included in the efficacy analyses. Additional efficacy analyses will be performed based on subjects who receive treatment with any amount of OPomd.

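### The population for overall and best overall response is defined in three conflicting ways, one of which admits subjects who never receive pomalidomide

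*Protocol*

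**What the plan says.** Three conditions stand in current text.

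- **At least one cycle of OPomd.** Protocol synopsis, Primary Analysis: "The primary efficacy analysis will be performed in all subjects that received at least one cycle of OPomd", with a baseline and at least one post-baseline disease assessment. This set is for ORR and BOR.
- **Any OPomd.** SAP 9.5.2, with the same rule in Protocol 13.4.3.2, includes "All subjects who receive treatment with any amount of the OPomd and have a baseline disease assessment and at least 1 post-baseline disease assessment". Both sections then add a second set without the assessment condition: "Additional efficacy analyses will be performed based on subjects who receive treatment with any amount of OPomd".
- **No OPomd condition.** Protocol 13.3.2: "Efficacy analyses of ORR and BOR will be performed using both the efficacy and safety population as defined previously". SAP 7.2 has the same sentence. Protocol 13.1.2 defines those sets: "The safety population is defined as all subjects who receive any amount of oprozomib, pomalidomide and/or dexamethasone", and the efficacy population as "subjects who are included in the safety evaluable population, and have a baseline disease assessment and at least 1 post-baseline disease assessment". SAP 6.2 removes roll-over subjects but otherwise keeps the rule: "included in the safety evaluable population, and have a baseline disease assessment and at least 1 post-baseline disease assessment".

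The parent set also varies. The synopsis describes the safety evaluable population as "all subjects who received any amount of the study treatment regimen oprozomib, dexamethasone and pomalidomide", which can be read as requiring all three drugs. Protocol 13.1.2 joins the drugs with and/or.

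The secondary objective in Protocol 4.2 concerns the efficacy of OPomd. Part 1 subjects start on Od and may add pomalidomide later (synopsis, Non-investigational Product; Protocol 9.3.1.1).

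**The concern.** A statistician programming the response tables cannot tell which denominator to use, and the choices differ in kind.

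The synopsis rule selects on an event after the start of treatment. It drops subjects who were assessed but stopped within the first cycle. Appendix D requires two consecutive assessments for a response, so such subjects will mostly be non-responders, and dropping them would tend to raise the rate.

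The rule in Protocol 13.3.2 and SAP 7.2 puts Part 1 subjects who never received pomalidomide into an analysis meant for the triplet. Protocol 13.4.3.2 and SAP 9.5.2 ask for results overall, by formulation, by dose cohort, and by formulation and dose cohort. They do not ask for a split by regimen. Under the wider sets, the overall and by-formulation rates could therefore mix Od with OPomd. For DLTs and adverse events, Protocol 13.4.2.1 and SAP 9.6.2 do require the two regimens to be kept apart.

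Efficacy is one of the inputs to the dose and formulation recommendation (synopsis, Primary Analysis), so the reader of an ORR needs to know which regimen it describes.

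**Working it through.** **1. Who qualifies under each rule**

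| Subject | Synopsis | 13.4.3.2 / SAP 9.5.2 lead set | 13.3.2 / SAP 7.2 efficacy set |
|---|---|---|---|
| OPomd for a full cycle, assessed | in | in | in |
| OPomd for less than a cycle, assessed | out | in | in |
| Part 1, later added pomalidomide for a full cycle, assessed | in | in | in |
| Part 1, never received pomalidomide, assessed | out | out | in |

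The last column uses the and/or wording of Protocol 13.1.2. Under the all-three-drugs reading of the synopsis, the last row would be out. The SAP 6.1 text available here shows only the roll-over safety set, so the check relies on Protocol 13.1.2 and SAP 6.2.

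**2. How many subjects the second row concerns**

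Efficacy assessments are every 4 weeks ± 1 week (Protocol 13.4.3.2) and a cycle is 28 days. A subject with less than one cycle but a post-baseline assessment must have had it early or at the end-of-study visit, which includes tumor assessments (10.2.20). The number is not given and is probably small.

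**3. How large the regimen mix could be**

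Inputs from Protocol 5.5.5: 45 evaluable for efficacy, 9 of them on Od; OPomd responders 20 of 28 (IR) and 3 of 8 (GR).

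- Reproducing the stated total: 9 + 28 + 8 = 45. The same passage also prints 23 for OPomd, but 9 + 23 = 32, so the formulation counts are used.
- Od share: 9/45 = 20%.
- OPomd, assessed: (20 + 3)/(28 + 8) = 23/36 = 63.9%, exact (Clopper-Pearson) 95% CI 46.2 to 79.2.
- Pooled, all 9 Od-only and none responding: 23/45 = 51.1% (35.8 to 66.3).
- Pooled, all 9 Od-only and all responding: (23 + 9)/45 = 32/45 = 71.1% (55.7 to 83.6).

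Od responses are not given, so the last two lines are limits and not estimates. If m of the 9 never received pomalidomide, the any-OPomd set has 45 − m subjects and the pooled set has 45. The two sets coincide when m = 0. The documents do not give m.

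**4. Assessed versus all treated with OPomd**

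Tables 1 and 2 show 39 subjects in the OPomd columns (IR 4 + 8 + 10 + 8 = 30, GR 4 + 5 = 9). If the 36 lie within the 39 and the other 3 are non-responders, the rate is 23/39 = 59.0% (42.1 to 74.4). This also needs a common data cutoff. The text of 5.5.5 states 21 August 2020, while the table notes state 02 December 2019 with a 21 August 2020 snapshot.

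On the same assumptions, the IR minus GR difference is 20/28 − 3/8 = 33.9 points (assessed) and 20/30 − 3/9 = 33.3 points (all treated).

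**The case against.** The intent is fairly clear. Protocol 13.3.2 and SAP 7.2 open by naming efficacy of the OPomd combination, the objective in 4.2 says the same, and the detailed methods in 13.4.3.2 and SAP 9.5.2 restrict to OPomd. The synopsis sends the reader to Section 13 for the full methods, which weakens it as a rival definition. Part 1 has its own cohorts, so dose-cohort rows may already separate the regimens. Section 5.5.5 reports response for OPomd on its own. Part 1 subjects who added pomalidomide meet the any-OPomd condition, possibly all of them. ORR is secondary, and Protocol 13.4.1 calls the analyses hypothesis generating.

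Most of this stands, and it limits the point. It does not remove the conflict. Section 13 contains both the OPomd-restricted and the unrestricted rule, and the SAP repeats both. The pair of sets in 13.4.3.2 resembles the pair in 13.3.2, but only the former requires OPomd. The overall and by-formulation rows remain open to mixing.

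A reader might infer that the sponsor plans to present a mixed rate as the OPomd result. The documents do not support that, because every statement of purpose concerns OPomd. A reader might also count the SAP's statement of no changes from the protocol (section 10) as a further error. It is not one: SAP 7.2 and 9.5.2 reproduce Protocol 13.3.2 and 13.4.3.2.

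**Conclusion.** The point holds as a conflict of wording that should be resolved. Three ORR/BOR populations stand in current text. One selects on completing a cycle, and one admits subjects outside the regimen named in the objective.

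The size is illustrative only. Against 63.9% in assessed OPomd subjects, pooling could give anything from 51.1% to 71.1%. That range assumes that all 9 Od subjects stayed Od-only and that 0 to 9 of them responded; it shrinks as more of them added pomalidomide. The 63.9% likewise equals the lead set of 13.4.3.2 only if no Part 1 subject added pomalidomide.

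It is tempting to read 51.1% to 71.1% as the effect of the defect, or to extend it to the full safety set. The documents support neither. They give neither the Od responses nor the number who added pomalidomide, and the safety-set count comes from tables with a different stated cutoff. The one-cycle rule probably affects few subjects, and no figure for it can be derived. The endpoint is secondary and descriptive. The MTD does not depend on it.

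**What to change.** - **Synopsis, Primary Analysis:** delete the one-cycle condition so that it matches Protocol 13.4.3.2 and SAP 9.5.2.
- **Protocol 13.3.2 and SAP 7.2:** state that ORR and BOR are analysed in the efficacy and safety populations restricted to subjects who received any OPomd. These are the two sets of 13.4.3.2 and SAP 9.5.2. The general efficacy rule in 13.1.2 and SAP 6.2 can stay as it is.
- **Synopsis and Protocol 13.1.2:** use one name and one wording for the safety (evaluable) population.
- **Efficacy tables:** report any Od-only response separately and keep it out of the OPomd, overall and by-formulation ORR, as 13.4.2.1 and SAP 9.6.2 already do for DLTs and adverse events.
- **Labelling:** say that the reconciliation was made after data were seen, because Protocol 5.5.5 already reports responses.

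The cost is a few sentences in each document and a regimen split in the efficacy tables. The lead set of 13.4.3.2 does not change, and no new data or subjects are needed.

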### **Final Analysis**

[figure not shown]
The objective of the final analysis is to provide an update on safety, tolerability and efficacy results. The final analysis will be based on subject data collected through study discontinuation or at the end of the study which includes the 30 day safety follow-up, whichever occurs first. The statistical methods used in the final analysis will be the same as those employed in the primary analysis, covering all study endpoints.

For a full description of statistical analysis methods, please refer to Section 13.

**Sponsor:** Amgen Inc.

## 2. Study Design and Treatment Schema

### Part 1 – Oprozomib + Dexamethasone (Od) 2/7 Schedule

[figure not shown]

 The Part 1 subjects will be allowed to add pomalidomide to their treatment, once there is a dose level of oprozomib determined to be safe in combination with pomalidomide and dexamethasone (as determined by the first cohort in Part 2).

 The estimated study duration for a participant is 12 months, approximately 4 weeks for screening and 10 months of treatment. 30 days after the last dose of oprozomib, the subject will return to the clinic for a safety follow-up visit.

### Study Design and Treatment Schema

#### Part 2 – Oprozomib + Pomalidomide + Dexamethasone (Opomd) 2/7 Schedule

 All subjects will be treated during the first week only, with a fixed, initial dose level of oprozomib (150 mg/day). For all dosing days thereafter the subjects will be treated with the appropriate dose level of oprozomib according to the dose escalation cohort evaluated.

 The evaluation of different formulations will start with IR (for the initial 1 to 2 dose levels) however, during the study, the two oprozomib formulations will be tested in parallel. The initial dose of the GR formulation will be determined by the data generated during the first cohorts of IR formulation escalation.

### 3. Study Glossary

Abbreviation or Term	Definition/Explanation
ADCC	antibody-dependent cytotoxic T-cell activity
AE	adverse event
ALP	alkaline phosphatase
ALT	alanine aminotransferase
ANC	absolute neutrophil count
AST	aspartate aminotransferase
AUC	area under the concentration-time curve
AUC inf	AUC from time 0 to the time extrapolated to infinity
AUC last	area under the curve until the last measurable concentration
BCRP	breast cancer-resistant protein
B/L	baseline
BLR	Bayesian Logistic Regression
BUN	blood urea nitrogen
C max	maximum observed concentration
CR	complete response
CrCl	creatinine clearance
CT	computed tomography
CT-L	chymotrypsin-like
CTCAE	Common Terminology Criteria for Adverse Events
DILI	drug induced liver injury
DLRM	dose level review meeting
DLRT	dose level review team
DLT	dose limiting toxicity
ECG	electrocardiogram
ECOG	Eastern Cooperative Oncology Group
eCRF	electronic case report form
EDC	electronic data capture
End of study for individual subject	defined as the last day that protocol-specified procedures are conducted for an individual subject
End of treatment	Last day of protocol specified treatment
End of study (primary completion)	defined as when the last subject is assessed or receives an intervention for the purposes of final collection of data for the primary endpoint(s)
End of study (end of trial)	defined as when the last subject is assessed or receives an intervention for evaluation in the study; if the study includes multiple parts (eg, safety follow-up or survival assessment), the end of study would include these additional parts

Abbreviation or Term	Definition/Explanation
Electronic Source Data (eSource)	source data captured initially into a permanent electronic record used for the reconstruction and evaluation of a trial.
FDA	Food and Drug Administration
GCP	good clinical practice
GI	gastrointestinal
GR	gastro-retentive
HBV	hepatitis B virus
HBcAb	hepatitis B core antibody
HCV	hepatitis C virus
HepBsAg	hepatitis B surface antigen
HepCAb	hepatitis C antibody
HIV	human immunodeficiency virus
ICF	informed consent form
ICH	International Conference on Harmonisation
IEC	Independent Ethics Committee
IPIM	investigational product instruction manual
IR	immediate release
IRB	Institutional Review Board
IUD	intrauterine device
IV	intravenous
IMWG	International Myeloma Working Group
LDH	lactate dehydrogenase
LSP	Lactation Surveillance Program
MDRD	modification of diet in renal disease
mg	milligram
MGUS	monoclonal gammopathy of undetermined clinical significance
mLRRMM	milliliter
	refractory multiple myeloma
MRI	magnetic resonance imaging
MTD	maximum tolerated dose
NASH	nonalcoholic steatohepatitis
NCCN	National Comprehensive Cancer Network
NCRM	new continual reassessment method
Od	oprozomib in combination dexamethasone
ODex	oprozomib in combination with dexamethasone
OPomd	oprozomib in combination with pomalidomide and dexamethasone
OPZ	oprozomib
ORR	overall response rate

Abbreviation or Term	Definition/Explanation
OS	overall survival (OS)
PBMC	peripheral blood mononuclear cell
PCR	polymerase chain reaction
PD	progressive disease
PFS	progression-free survival
PK	pharmacokinetics
PO	per os – by mouth
PPI	proton pump inhibitor
PR	partial response
PSP	Pregnancy Surveillance Program
PT	prothrombin time
PTT	partial thromboplastin time
RBC	red blood cell
RP3D	recommended formulation and Phase 3 dose
SAE	serious adverse event
sCR	stringent complete response
Source Data	information from an original record or certified copy of the original record containing patient information for use in clinical research. The information may include, but is not limited to, clinical findings, observations, or other activities in a clinical trial necessary for the reconstruction and evaluation of the trial. Source data are contained in source documents (original records or certified copies). (ICH Guideline (E6)). Examples of source data include Subject identification, Randomization identification, and Stratification Value.
Study day 1	defined as the first day that protocol specified investigational product(s)/protocol-required therapies is/are administered to the subject
SPEP	serum protein electrophoresis
$t_{1/2}$	terminal elimination half-life
TBIL	total bilirubin
TLS	tumor lysis syndrome
$T_{\max}$	time when maximum plasma concentration is reached
ULN	upper limit of normal
UPEP	urine protein electrophoresis
US	United States
VGPR	very good partial response
WBC	white blood cell

## 4. OBJECTIVES

### 4.1 Primary

- Identify the maximum tolerated dose (MTD) of oprozomib formulations in combination with pomalidomide and dexamethasone (OPomd) in subjects with relapsed or refractory multiple myeloma
- Evaluate the safety and tolerability of the OPomd combination in subjects with relapsed or refractory multiple myeloma

### 4.2 Secondary

- Characterize the pharmacokinetics (PK) of oprozomib
- Evaluate the efficacy of OPomd according to International Myeloma Working Group (IMWG) uniform response criteria
- Identify the recommended formulation and recommended formulation and Phase 3 dose (RP3D) of oprozomib in combination with pomalidomide and dexamethasone in subjects with relapsed or refractory multiple myeloma

## 5. BACKGROUND AND RATIONALE

### 5.1 Multiple Myeloma Background

Multiple myeloma is a neoplastic plasma-cell disorder that is characterized by clonal proliferation of malignant plasma cells in the bone marrow microenvironment, monoclonal protein in the blood or urine and associated organ dysfunction (Palumbo and Anderson, 2011). Multiple myeloma accounts for almost 2% of all cancers and 20% of hematologic malignancies. The disease is slightly more common in males and African Americans (Siegel, 2015). Multiple myeloma remains an incurable cancer, although recent improved understanding of pathogenesis of myeloma has led to the development of new treatments and improved survival (Smith and Yong, 2013).

Myeloma arises from an asymptomatic premalignant proliferation of monoclonal plasma cells that are derived from post-germinal center B cells. Multistep genetic and micro-environmental changes lead to the transformation of these cells into a malignant neoplasm. Myeloma is thought to evolve most commonly from a monoclonal gammopathy of undetermined clinical significance (MGUS) that progresses to smoldering myeloma and ultimately to symptomatic myeloma.

The uncontrolled growth of myeloma cells has many consequences, including skeletal destruction, bone marrow failure, increased plasma volume and viscosity, suppression of normal immunoglobulin production, and renal insufficiency (Durie, 2011).

Symptomatic (active) disease should be treated immediately and the age of the patient guides the treatment strategy. Current data support the initiation of a three-drug regimen induction therapy (eg., bortezomib, thalidomide and dexamethasone) plus hematopoietic stem cell transplantation for patients under the age of 65 years who do not have substantial heart, lung, renal, or liver dysfunction. Autologous stem cell transplantation with a reduced-intensity conditioning regimen should be considered for older patients or those with coexisting conditions. Conventional therapy combined with thalidomide, lenalidomide, or bortezomib should be administered in patients older than 65 years of age. Less intensive approaches that limit toxic effects or prevent treatment interruption that would reduce the intended treatment effect should be considered in patients over 75 years of age or in younger patients with coexisting conditions. Biologic age, which may differ from chronologic age and the presence of coexisting conditions should determine treatment choice and drug dose (Palumbo and Anderson, 2011).

Despite advances in the management of multiple myeloma as described, relapse is inevitable in almost all patients. Recurrence of myeloma is typically more aggressive with each relapse, leading to the development of treatment-refractory disease, which is associated with a shorter survival (Dimopoulos, 2014). More treatment options are still warranted. Treatment of relapsed or refractory multiple myeloma (RRMM) presents a special therapeutic challenge, due to the heterogeneity of disease at relapse and the absence of clear biological based recommendations regarding the choice of salvage therapies at various time points of disease progression. With increasing recognition of the inherent clonal heterogeneity and genomic instability of the plasma cells influencing both inherent and acquired therapeutic resistance, the identification of the optimal choice and sequence of therapies has become critical. Several new agents and targets are currently under development and show considerable promise. Along with carfilzomib and pomalidomide that were approved by US FDA in 2012 and 2013 respectively, four additional agents including daratumumab, elotuzumab, ixazomib and panobinostat were approved by the US FDA for RRMM in 2015. Next generation proteasome inhibitors (PIs) (marizomib and oprozomib) and other molecularly targeted therapies directed at specific cell signaling pathways (including PI3K/AKT/mTOR inhibitors, Hsp90 inhibitors, cell cycle inhibitors, kinesin spindle protein inhibitors) are currently in development.

Even newer approaches such as monoclonal antibodies targeting CD138, and others have also demonstrated promising anti-myeloma activity (Nooka, 2015).

